D1. Overview: We propose a brief proof-of-principle, mechanistic trial to determine whether interventions that target cognitive pain modulation (BAT) and pain-related brain networks (tDCS) will normalize pain modulatory balance and pain-related cerebral activation, thereby reducing clinical pain and disability, and ethnic differences therein. In a fully factorial design, we will randomize 360 adults (180 AA, 180 NHW) with knee OA to one of four conditions created by crossing Real tDCS vs. Sham tDCS with Real BAT vs. Sham BAT (**Table 1**). This is a two-site study conducted at the University of Florida (UF) and the University of Alabama at Birmingham (UAB). Equal numbers of participants will be recruited at each site. At the UF site we will offer potential participants the option of the study team arranging travel to the study site via Uber Health. Using the REDCap randomization module, we will block randomize with stratification for site, sex, and race in double blind fashion. After initial eligibility screening, each participant will complete two baseline assessments, including clinical measures, QST, and neuroimaging. After being randomized to one of the four treatment conditions, participants will undergo a five-day intervention period. On the last intervention day after the final treatment, participants will undergo post-treatment clinical, QST and brain imaging assessments. The timing of study activities throughout the protocol is depicted in **Table 2**. In order to assess persistence of treatment effects, participants will complete follow-up online or telephone assessments of clinical pain and disability each month for three months after completion of treatment.

Table 1. Treatment Conditions

	Real tDCS	Sham tDCS
Real BAT	90 Adults (45 AA, 45 NHW)	90 Adults (45 AA, 45 NHW)
Sham BAT	90 Adults (45 AA, 45 NHW)	90 Adults (45 AA, 45 NHW)

Participants will be paid up to \$350 for completing the entire protocol, which is itemized as follows:

Study Activities	Baseline		Treatment					Monthly Follow-Up		
	Visit 1	Visit 2	Visit 3	Visit 4	Visit 5	Visit 6	Visit 7	1-Mo	2-Mo	3-Mo
Informed Consent	X									
Baseline Questionnaires	X	X					X			
Activity Tests	X						X			
Sensory & Pain Tests	X						X			
Brain Imaging		X					X			
Tx Questionnaires			X	X	X	X	X			
Treatment Session			X	X	X	X	X			
Pain Assessment			X	X	X	X	X			
Follow-Up Questionnaire								X	X	X

- Baseline Session 1 (\$50)
- Baseline Questionnaires (\$20)
- Baseline Session 2 (\$50)

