Socioeconomic status (SES): Using address information provided by the participant, we will access publicly available online tools that allow us to derive geographically-based metrics, such as the area deprivation index (ADI)⁵⁸, as well as measures of residential segregation and potentially other census-based measures that reflect social determinants of health and poverty.

Literacy Testing: We will conduct a brief test to measure the participant's ability to read common medical words (the REALM-R¹¹), in order to determine whether the participant may need assistance with completing questionnaires.

Clinical Pain and Function: In order to determine the effects of the intervention on pain, we will assess clinical pain at the beginning and end of each intervention study visit with Numerical Rating Scale (NRS) assessing current pain from 0 (no pain) to 100 (most intense pain imaginable), as in our previous pilot trial (4). In addition, at baseline and post-treatment we will also assess clinical pain and self-reported function using the following symptom questionnaires: Western Ontario and McMaster Universities Osteoarthritis Index (WOMAC)¹², which will be our primary clinical measure, and the Graded Chronic Pain Scale. To assess functional performance pre- and post-treatment, the Short Physical Performance Battery (SPPB) will be completed. This measure is widely used in older populations to assess lower extremity function (58, 59).

Psychosocial Measures: We will ask participants to complete the following questionnaires that assess pain-related psychosocial factors: the Pain Catastrophizing Scale (PCS) consists of 13 items assessing three components of catastrophizing: rumination, magnification, and helplessness (61); the Perceived Stress Scale (PSS)-14 is a 14-item instrument that assesses individuals' subjective level of stress related to different types of life stress and has documented validity and reliability (64, 65); the Freiburg Mindfulness Inventory (FMI) will be administered to assess mindfulness at baseline and following treatment (66). In order to examine additional clinical and psychosocial factors that may predict treatment response, we will also administer: the Positive and Negative Affect Scale (PANAS, State and Trait versions), the PROMIS Sleep disturbance 8b & Sleep Related Impairment questionnaires, and the MoCA.

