
We recognize that scheduling five daily visits is a challenge, and we expect missed visits for some participants. If participants miss only one of five visits, that will not be considered a protocol deviation; however, if they miss two or more visits, this will be reported as a minor deviation.

Additional Post-Treatment Measures: We will assess the following measures post-treatment. 1) Side Effects: Participants will complete a brief questionnaire assessing side effects of treatment, including side effects that can occur with tDCS (e.g. tingling, itching, headache, fatigue) or mindfulness (breathing changes, dizziness, sleep changes, anxiety). And participants will be asked whether they believe they received real or sham tDCS. 2) Treatment Satisfaction/Helpfulness: Participants will provide a rating of overall satisfaction with treatment, and a rating of how helpful they found the treatment for reducing their pain. 3) Three-Month Follow-Up: Each month for three months post-intervention, participants will complete a follow-up questionnaire, including the NRS assessing average pain over the past 24 hours, as well as ratings of pain interference and mood. We will also administer the PSS and the PCS at these follow-up time points. At the final follow-up assessment, we will ask participants to report on their global impression of treatment helpfulness and to indicate

whether and how often they continue to use their BAT skills. 4) **Debriefing:** After the final follow-up assessment, one of the research team members will telephone the participant to explain the purpose of the study. At this time, we will not be able to reveal which tDCS group they were in, as the investigators will remain blind to this. In addition, we will not reveal which BAT condition they received, because if participants communicate such information to others who are in the study, this could bias study results. Interested participants will be directed to online resources to learn more about mindfulness.

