where BAT and tDCS are dummy variables for interventions, AA is the dummy variable for African Americans. Linear contrast will be employed to test the main effect of BAT (corresponds to the test of $\beta_3 + \beta_6/2 + \beta_7/2 + \beta_9/4=0$) and tDCS (test of $\beta_4 + \beta_6/2 + \beta_8/2 + \beta_9/4=0$). These six tests (2 main effects for three primary outcomes) will be performed at one-sided $\alpha=0.0083$ significance level. In addition, point estimates and 95% confidence intervals will be obtained for the BAT and tDCS effects with or without the presence of the other treatment in the whole population or within AA and NHW subgroups. We will use normal probability plots to assess distributional assumptions of the models. The above analysis plan will be followed for other outcomes including resting state cerebral blood flow, disability and functional performance, as well as the analysis of changes of the outcomes from post-treatment to three-month follow-up.

For **Aim 2**, we will assess interactions between race and intervention. Point estimates and 95% confidence intervals will be obtained for the race difference in the effects of BAT and tDCS on each outcome. Because we expect the interaction effect to be smaller than the main effect, for formal hypothesis testing, we plan to pool evidence across three primary outcomes to test the ethnic group differences. Specifically, we will obtain a p-value corresponding to test the hypothesis $\beta_7=\beta_8=\beta_9=0$ for

each outcome based on the general linear model specified in the analysis plan for Aim 1. And Fisher's combination of three p-values will be used as the overall test statistic, which will be compared to the null distribution obtained through permutation of ethnic group variable.

For Aim 3, path models with strictly ordered relationships will be used to study the interventions' direct effects on clinical pain and disability and the indirect effect on the mediating variables including pain modulatory balance; resting state and stimulus-evoked pain-related brain function; perceived stress, pain catastrophizing, and mindfulness. We will construct additional analyses using pre-treatment variables as predictors of intervention effects. We will examine separate multivariable models for each ethnic group to determine whether mediators of treatment effects differ for AAs vs. NHWs.

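### No pain or disability instrument is listed at both post-treatment and months 1–3, so the planned change to three months cannot be formed, and that contrast measures decay, not retained benefit

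*Combined protocol and SAP*

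**What the plan says.** **Purpose.** D1 (Overview) gives the reason for follow-up: "In order to assess persistence of treatment effects, participants will complete follow-up online or telephone assessments of clinical pain and disability each month".

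**Before and just after treatment.** D2.1, Clinical Pain and Function, has a "Numerical Rating Scale (NRS) assessing current pain from 0 (no pain) to 100 (most intense pain imaginable") at the start and end of each intervention visit. It then states that "at baseline and post-treatment we will also assess clinical pain and self-reported function using the following symptom questionnaires": WOMAC, "which will be our primary clinical measure, and the Graded Chronic Pain Scale". The SPPB is taken pre- and post-treatment.

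**Months 1–3.** The Three-Month Follow-Up item under Additional Post-Treatment Measures describes a questionnaire "including the NRS assessing average pain over the past 24 hours, as well as ratings of pain interference and mood". PSS and PCS are added.

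**Analysis.** D3, Statistical Analysis Plan, Aim 1, extends the factorial general linear model to other outcomes and to "the analysis of changes of the outcomes from post-treatment to three-month follow-up". That model contains a BaselineScore term. The plan does not say which value fills it in the change analysis, and it does not name a comparison of arms on the month-3 level.

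**The concern.** A change score needs the same measure at both ends. For clinical pain, the listed measures differ in instrument (WOMAC or Graded Chronic Pain Scale against an NRS) or in recall (current pain against a 24-hour average). For disability, no scale used earlier is listed again. Subtracting one from another would mix constructs, and the plan gives no linking rule.

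The second difficulty lies in the contrast. The post-treatment value is already affected by treatment, so change from that point asks how much benefit was lost, while D1 asks whether the benefit is still there. A reader given only a non-significant change could not tell a lasting benefit from none at all.

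At stake is the clinical question for which the three monthly contacts are made. Items not asked at the time cannot be recovered later.

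**Working it through.** **1. Instruments side by side** (D2.1, the study activities table in D1, and the Three-Month Follow-Up item)

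| Measure | Baseline | Treatment visits | Post-treatment | Months 1–3 |
|---|---|---|---|---|
| WOMAC | listed | – | listed | not listed |
| Graded Chronic Pain Scale | listed | – | listed | not listed |
| SPPB | listed | – | listed | not listed |
| NRS, current pain | – | listed | listed (end of Visit 7) | not listed |
| NRS, 24-hour average | not listed | not listed | not listed | listed |
| Pain interference, mood ratings | not tied to an earlier instrument | – | not tied to an earlier instrument | listed |

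The activities table shows no sensory testing, activity tests or imaging at months 1–3, so clinical pain and disability are the only Aim 1 outcomes to which a three-month analysis could apply. No row for either is listed at both post-treatment and follow-up. For the 24-hour item there is no listed baseline value to enter as BaselineScore. PSS and PCS are repeated, but Aim 3 treats them as mediators.

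**2. The plan's own power figure.** The plan gives none for follow-up. Table 4 gives power 0.90 for the tDCS pain rating (D = 0.44) with 320 completers, that is 160 against 160 for a main effect, at α = 0.05/6 = 0.0083. Two-sided, the critical value is 2.64:

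- D = 0.44: 0.44 × √(160/2) = 3.94; Φ(3.94 − 2.64) = 0.90. Reproduced.
- D = 0.39: 0.39 × √80 = 3.49; Φ(3.49 − 2.64) = 0.80. Reproduced.

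(Aim 1 calls the tests one-sided, whereas Table 4 matches two-sided tests. That is a separate discrepancy and does not affect this point.)

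**3. What the change contrast estimates.** Let d₀ be the effect post-treatment and d₃ the effect at month 3, in SD units with benefit positive. For raw change, or change adjusted for the pre-treatment value, the arm contrast is

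d₃ − d₀.

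Assumptions not in the documents: one instrument throughout, equal SDs, d₀ = 0.44 and correlation r = 0.5 between times. The SD of change is then √(2(1 − r)) = 1. The last two columns compare arms on the month-3 level.

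| Scenario | Change contrast | Rejection rate | Month-3 level | Rejection rate |
|---|---|---|---|---|
| Full persistence | 0.44 − 0.44 = 0 | 0.008 | 0.44 | 0.90 |
| Half persistence | 0.22 − 0.44 = −0.22 | 0.25 | 0.22 | 0.25 |
| No persistence | 0 − 0.44 = −0.44 | 0.90 | 0 | 0.008 |
| Never an effect | 0 − 0 = 0 | 0.008 | 0 | 0.008 |

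For r from 0.3 to 0.7, the change-contrast power runs from 0.16 to 0.46 under half persistence and from 0.75 to 0.99 under no persistence. The zeros do not move.

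A simulation of the plan's factorial model and its tDCS contrast (2,000 runs, correlations 0.5) agrees. Under full persistence the change estimate was −0.002 with 0.8% rejections; with no effect at any time it was −0.003 with 0.6%. Comparing arms at month 3 with a same-item baseline covariate gave power 0.97 under full persistence.

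**4. If BaselineScore means the post-treatment value.** The contrast becomes d₃ − r·d₀. Under full persistence it is 0.44 − 0.7 × 0.44 = 0.13 for r = 0.7 and 0.44 − 0.5 × 0.44 = 0.22 for r = 0.5. That is no longer null, but it is not the retained 0.44. With r = 0.5, half persistence gives 0.22 − 0.22 = 0.

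**The case against.** The follow-up list is open: it begins with the word for partial enumeration, and the activities table does not itemise its questionnaires. D1 promises disability follow-up, and the interference rating may be what was meant. A reader might infer that the 24-hour item is never asked earlier, or that WOMAC is never asked at follow-up. The documents support only that neither is listed. This stands, but a plan that relies on unlisted items should list them.

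A reader might also infer that persistence cannot be estimated at all. That goes too far. The arms are randomised, so the monthly 24-hour NRS can be compared between them without a same-item baseline, at a cost in precision and not in validity. It is simply not the analysis planned.

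Nor is change from post-treatment an illegitimate contrast. It measures decay, and zero means no decay. With a common instrument, adding it to the post-treatment effect that Aim 1 already estimates gives the month-3 effect. What remains is that the change test read alone cannot support persistence, and that the month-3 contrast should be named.

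Finally, D2 says this is not an efficacy trial and puts the main interest in brain function and pain modulatory balance. Aim 1's primary tests do not depend on the follow-up questionnaires. That limits the weight of the point.

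**Conclusion.** The point holds as a gap in a secondary objective. From the listed measures, the planned change from post-treatment to three months cannot be formed for clinical pain or disability. This rests on reading the instrument lists as written and needs no numerical assumption.

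If a common instrument were supplied, the contrast would still be a loss-of-effect measure: 0, −0.22 and −0.44 SD for full, half and no persistence, and 0 when there was never an effect. These sizes are illustrative. The 0.44 is the pilot tDCS pain-rating effect in Table 4, neither a WOMAC nor a BAT effect, and equal SDs are assumed. The zero under full persistence applies to raw or pre-treatment-adjusted change; adjustment for the post-treatment value gives 0.13 to 0.22 SD for assumed correlations of 0.7 to 0.5.

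This should be fixed, but no primary conclusion depends on it.

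**What to change.** 1. Add WOMAC to the 1-, 2- and 3-month questionnaires. Add the 24-hour-average NRS and the interference items to baseline and Visit 7 (or the separate post-treatment session where one is used). If any of these are already collected, list them.
2. Prespecify the arm difference at each month, adjusted for the pre-treatment value of the same measure, as the persistence estimate. Either a repeated-measures model or an ANCOVA at each month will serve.
3. Keep change from post-treatment as a supplementary loss-of-effect analysis, and state which value enters as BaselineScore.
4. For participants already past the relevant visits, compare arms on the monthly 24-hour NRS level, adjusting for baseline WOMAC.

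The cost is a few minutes of questionnaire time at existing contacts, with no added visit. Participants past Visit 1, Visit 7 or follow-up when the change is made will lack the corresponding added items.

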SA2: To determine ethnic group differences in the independent and combined effects of brief BAT and tDCS interventions (vs. their respective sham conditions) on pain modulatory balance, pain-related brain function, and OA-related pain and disability among AA and NHW adults with symptomatic knee OA.

Hypothesis 2: Real BAT and tDCS, independently and in combination, will produce: 1a) Greater improvements in pain modulatory balance among AAs compared to NHWs; 1b) Greater decreases in resting and pain-evoked cerebral blood flow in pain-related ROIs among AAs compared to NHWs; and 1c) Greater improvements in clinical pain, self-reported disability, and functional performance among AAs compared to NHWs. We anticipate that the combined treatments will produce the largest benefits for AAs compared to NHWs. We expect more robust treatment effects among AAs, as our previous findings suggest that the risk factors targeted by these treatments produce greater adverse consequences among AAs with knee OA.

SA3: To identify biopsychosocial predictors and mediators of treatment-related improvements in clinical pain and disability following BAT and tDCS among AAs and NHWs with symptomatic knee OA.

Hypothesis 3: Improvements in clinical pain and disability following BAT and tDCS will be mediated by treatment-induced adaptive changes in: 3a) Pain modulatory balance assessed via QST; 3b) Resting state and stimulus-evoked pain-related regional cerebral blood flow; and 3c) Perceived stress, pain catastrophizing, and mindfulness. In addition, we will conduct analyses to identify pre-treatment variables that predict treatment response, including pain-related brain structure and function, pain modulatory balance, and psychosocial variables. We will examine separate multivariable models for each ethnic group to identify mediators and predictors of treatment effects that differ for AAs vs. NHWs.

6. Research Plan:

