Resilience Measures: In order to investigate whether resilience predicts responses to our interventions, we will administer several pre-treatment resilience measures. These include: the Pain Resilience Scale, the PROMIS Positive Affect & Well-Being Scale, PROMIS Support Scale, the Life Orientation Test-Revised, the Adult Hope Scale, and the PROMIS Sleep Disturbance Scale 8a.

Post-treatment measures of clinical pain/function, QST measures, and brain imaging will be re-assessed after the final intervention session. In order to accommodate participant and clinic schedules, some participants will complete these measures on Day 5, immediately after the intervention. For other participants, some or all of the measures may be completed in a separate session within a few days of the final intervention.

Baseline Session 1

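### Aim 3 plans to judge ethnic differences in mediators and predictors from separate models per group, names no test or interval for the difference, and does not state when mediators and outcomes are measured

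*Combined protocol and SAP*

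**What the plan says.** Section 5, SA3, sets out the comparison for both mediators and predictors: "We will examine separate multivariable models for each ethnic group to identify mediators and predictors of treatment effects that differ for AAs vs. NHWs". Section D3 repeats it for mediators under Aim 3: "We will examine separate multivariable models for each ethnic group to determine whether mediators of treatment effects differ for AAs vs. NHWs". The model type is given as follows: "For Aim 3, path models with strictly ordered relationships will be used to study the interventions' direct effects on clinical pain and disability". Aim 3 states no alpha, no power, no rule for declaring a group difference, and no time points for mediators or outcomes. D3 nevertheless counts it among the three primary aims for which inference is planned.

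The nearest formal comparison of the ethnic groups is in Aim 2. There the race-by-treatment terms are tested for each of the three primary outcomes, and "Fisher's combination of three p-values will be used as the overall test statistic".

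On timing, D1 says: "On the last intervention day after the final treatment, participants will undergo post-treatment clinical, QST and brain imaging assessments". D2.1 adds some latitude: "For other participants, some or all of the measures may be completed in a separate session within a few days of the final intervention". D2.1 names WOMAC as the primary clinical measure and schedules it at baseline and post-treatment. The mindfulness inventory is also taken at baseline and after treatment. The monthly follow-up itemised in D2.2 lists NRS pain, pain interference, mood, the PSS and the PCS, but not WOMAC.

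**The concern.** A model fitted within one group shows whether a path can be distinguished from zero in that group. Two such models, set side by side, do not show whether the paths differ from each other. With half the sample in each, a path of the same size can easily reach significance in one group and miss it in the other. Without a stated comparison, a reader of the results is likely to treat that pattern as evidence of a race-specific mechanism. For this trial that would be a substantive and sensitive claim.

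Timing raises a second, smaller question. A path model with an assumed order needs data that carry some information about order. For WOMAC with the QST, imaging and mindfulness mediators, the schedule gives one shared post-treatment assessment and does not fix which is measured first.

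**Working it through.** **The plan's own figures.** Aim 3 has none. The figures in D3 belong to Aim 1, and they reproduce with a two-sided alpha of 0.05/6. Power = Φ(d√N/2 − 2.638). For d = 0.34 and N = 320: 0.34 × 17.889/2 = 3.041, 3.041 − 2.638 = 0.403, power 0.656 (Table 4: 0.65). For d = 0.44, 0.51 and 0.82 the results are 0.903, 0.973 and above 0.99 (Table 4: 0.90, 0.98, 0.99). Detectable effect at 80% power: (2.638 + 0.842) × √(4/320) = 0.389 (stated 0.39).

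**Group sizes.** 320 expected completers / 2 = 160 per ethnic group. Imaging is planned in about two-thirds: 320 × 2/3 / 2 ≈ 107 per group (106 was used in the simulation to keep the arms equal).

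**Does Aim 2 fill the gap?** Its test sets β7 = β8 = β9 = 0 for pain modulatory balance, pain-evoked activation and clinical pain. For the first two this bears on the treatment-to-mediator step. It does not test any mediator-to-pain path, any indirect effect, or the psychosocial mediators.

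**Chance of a discordant pair when mediation is identical.** If each group reaches significance with probability p, exactly one does so with probability 2p(1−p): 0.42 at p = 0.3, 0.50 at 0.5, 0.32 at 0.8, 0.18 at 0.9.

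**Simulation to obtain p.** The inputs are a treatment-to-mediator effect from Table 4, an assumed mediator-to-outcome path of 0.3, an assumed direct effect of 0.1 and unit residual SDs. There is one two-level treatment and one mediator, with 4,000 replicates. Mediation is declared in a group when both paths are significant at two-sided 0.05. The direct test is (indirect effect in group 1 − indirect effect in group 2) divided by its delta-method standard error. Power of the direct test is for mediation present in one group only (treatment-to-mediator effect zero in the other).

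| Per group | d | Significant in a group | Exactly one group (false difference) | Direct test, false positive | Direct test, power |
|---|---|---|---|---|---|
| 160 | 0.34 | 55% | 50% | 4% | 24% |
| 160 | 0.44 | 76% | 36% | 4% | 37% |
| 160 | 0.51 | 86% | 25% | 4% | 46% |
| 160 | 0.82 | 96% | 8% | 4% | 77% |
| 106 | 0.34 | 36% | 46% | 3% | 13% |
| 106 | 0.44 | 53% | 49% | 3% | 22% |
| 106 | 0.51 | 64% | 46% | 4% | 27% |
| 106 | 0.82 | 84% | 27% | 4% | 55% |

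The 8% cell pairs d = 0.82, which Table 4 gives for cerebral blood flow, with the full-sample size. At the imaging size the same effect gives 27%.

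**Timing.** Suppose the true order is treatment, then pain, then mediator, with no mediation. Assume pain d = 0.44 and a pain-to-mediator path of 0.3 to 0.5. A same-assessment path model then declares mediation in 21–41% of trials with n = 320 and 13–24% with n = 160. Now take 1-month pain as the outcome, assuming pain persistence of 0.5 to 0.7. With n = 320, a lagged model that leaves out post-treatment pain still declares mediation in 15–43% of trials. Including post-treatment pain brings this to 1–3%.

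**The case against.** The two ethnic groups are independent samples, so separate models supply the estimates and standard errors that a difference test needs. An unconstrained multi-group model fits the same parameters. The plan also never says that significance in one group only will count as a difference. This stands: the defect is a missing comparison, and the 8–50% applies only if the gap is filled by comparing significance. It does not remove the point, because the separate models are the only stated means of deciding whether mediators differ.

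The size depends on power that the documents do not give. At 95% power per group the discordance is 2 × 0.95 × 0.05 = 9.5%. This also stands, and is why a range is shown.

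A reader might infer that all Aim 3 mediators and outcomes come from one assessment. The documents do not say so. Aim 3 names no time points, some measures may be taken days later, NRS pain is recorded at every treatment visit, and NRS pain, interference, PSS and PCS are collected monthly. The supported statement concerns WOMAC and the mediators measured with it.

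A reader might also infer that the trial's main conclusion is at risk. D2 puts the primary mechanistic interest in changes in brain function and pain modulatory balance, and the six alpha-controlled tests belong to Aim 1.

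Finally, moving the main mediated outcome to 1-month pain looks like a cure for the ordering problem. It would displace WOMAC, leave out WOMAC disability, and, without adjustment for post-treatment pain, leave much of the false mediation in place.

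**Conclusion.** The concern holds for the between-group comparison. As written, Aim 3 cannot support a statement that mediators or predictors differ between African American and non-Hispanic white participants, because it names neither a test nor an interval for that difference, and Aim 2 does not supply one for indirect effects. If the difference were judged by which paths are significant, equal mediation would look unequal in roughly 8–50% of trials, against 3–4% for a direct test. Those figures rest on the assumed mediator-to-outcome path of 0.3, Table 4 effects applied equally to both groups, a single-mediator model and two-sided 0.05.

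On timing the finding is narrower: the time points are unstated, and WOMAC mediation through QST, imaging or mindfulness rests on a shared assessment that cannot establish order. The primary inference under Aim 1 is not affected.

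**What to change.** In the D3 text for Aim 3, and to match in SA3:

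- Fit one multi-group or race-moderated path model. For each indirect effect, report the African American minus non-Hispanic white difference with a bootstrap confidence interval.
- Test predictors through predictor × treatment × race terms.
- Claim a race difference only from these results. Keep the group-specific models as descriptive.
- State the time point of every mediator and outcome. Keep WOMAC pain and disability as the main mediated outcomes, and say that same-assessment mediation does not establish order.
- Add a sensitivity analysis: 1-month NRS pain on Visit 7 mediators, adjusted also for post-treatment pain.

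The data are already planned, so the cost is SAP wording and modest analysis work. The main downside is power: about 13–77% for the direct test when only one group has mediation. Fewer race differences could be claimed, and interval widths should be reported so that a null result is not read as equality. The lagged model has its own limits. Follow-up NRS asks about the past 24 hours, whereas the treatment-visit NRS asks about current pain, so adjustment for post-treatment pain will be imperfect. Lagging also does not remove confounding between mediator and outcome.
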